## 1. INTRODUCTION

This statistical analysis plan (SAP) describes the statistical analysis methods and data presentations to be used in tables, figures, and listings (TFLs) in the clinical study report (CSR) for Study GS-US-417-0303. This SAP is based on the study protocol Amendment 1 dated 05 July 2016 and the electronic case report form (eCRF). The SAP will be finalized before database finalization of Week 24 Analysis. Any changes made after the finalization of the SAP will be documented in the CSR.

### 1.1. Study Objectives

The primary objective of this study is as follows:

- To evaluate the effects of filgotinib in combination with MTX versus MTX alone for the treatment of signs and symptoms of rheumatoid arthritis (RA) as measured by the proportion of subjects achieving an American College of Rheumatology 20% improvement response (ACR20) at Week 24

The secondary objectives of this study are as follows:

- To evaluate the effect of filgotinib in combination with MTX versus MTX alone on physical function as measured by change from Baseline in the Health Assessment Questionnaire Disability Index (HAQ-DI) score at Week 24
- To evaluate the effects of filgotinib in combination with MTX versus MTX alone for the treatment of signs and symptoms of RA as measured by the proportion of subjects achieving Disease Activity Score for 28 joint count using CRP (DAS28 [CRP])<2.6 at Week 24
- To evaluate the effects of filgotinib alone versus MTX alone for the treatment of signs and symptoms of RA as measured by the proportion of subjects achieving ACR20 at Week 24
- To evaluate the effect of filgotinib alone versus MTX alone on physical function as measured by change from Baseline in HAQ-DI score at Week 24
- To evaluate the effects of filgotinib alone versus MTX alone for the treatment of signs and symptoms of RA as measured by the proportion of subjects achieving DAS28 (CRP)<2.6 at Week 24
- To evaluate the effects of filgotinib in combination with MTX versus MTX alone on preservation of joint structure as measured by change from Baseline in the mTSS at Week 24 and 52
- To evaluate the effects of filgotinib alone versus MTX alone on preservation of joint structure as measured by change from Baseline in modified Total Sharp Score (mTSS) at Week 24 and 52

- To evaluate the safety and tolerability of filgotinib alone and in combination with MTX
- To evaluate the effects of filgotinib alone and in combination with MTX on work productivity, fatigue, and general quality of life as measured by Short-Form Health Survey, 36 Questions (SF-36), Functional Assessment of Chronic Illness Therapy-Fatigue (FACIT-Fatigue), EuroQol 5 Dimensions (EQ-5D) and Work Productivity and Activity Impairment for RA (WPAI-RA)

The exploratory objectives of this study are as follows:

- [REDACTED]
- [REDACTED]
- [REDACTED]

## 1.2. Study Design

[figure not shown]
This is a randomized, double-blind, placebo- and active-controlled, add-on, Phase 3 study in adult male and female subjects with moderately to severely active RA who have limited or no prior exposure to MTX therapy. The study is designed to evaluate the efficacy, safety and tolerability of filgotinib as well as its effect on patient-reported outcomes, including work productivity, fatigue, and quality of life. In addition, PK will be assessed.

Approximately 1200 subjects will be randomized in a 2:1:1:2 ratio to filgotinib 200 mg plus MTX, filgotinib 100 mg plus MTX, filgotinib 200 mg alone, or MTX alone, for up to 52 weeks:

- Filgotinib 200 mg + MTX group: filgotinib (200 mg once daily [q.d.]) + PTM filgotinib 100 mg (PTM q.d.) + MTX (once weekly up to 20 mg) (N=400)
- Filgotinib 100 mg + MTX group: filgotinib (100 mg q.d.) + PTM filgotinib 200 mg (PTM q.d.) + MTX (once weekly up to 20 mg) (N=200)
- Filgotinib 200 mg monotherapy group: filgotinib (200 mg q.d.) + PTM filgotinib 100 mg (PTM q.d.) + PTM MTX (PTM once weekly) (N=200)
- MTX monotherapy group: PTM filgotinib 100 mg (PTM q.d.) and PTM filgotinib 200 mg (PTM q.d.) + MTX (once weekly up to 20 mg) (N=400)

Randomization will be stratified by geographic region and presence of rheumatoid factor (RF) or anti-cyclic citrullinated peptide antibody (anti-CCP Ab) at screening.

**Figure 1-1. Study Design**

At Week 24, subjects who have not achieved at least 20% improvement from Day 1 in both swollen joint count (SJC) and tender joint count (TJC) will discontinue investigational study drug dosing but will continue with study visits and assessments per protocol. All subjects meeting this criterion who discontinue from investigational therapy are to receive standard of care treatment for their RA as determined by the investigator.

All subjects who attain responder status at Week 24 will continue on their assigned study drug, in a blinded fashion through Week 52. Placebo-responders at Week 24 will continue on placebo in a blinded fashion through Week 52.

All subjects who have received at least one dose of study drug and exit the study early will complete an early termination (ET) visit at the time of study discontinuation, with a follow up visit four weeks after the last dose of study drug (Post Treatment visit Week 4), regardless of dosing duration.

At completion of the 52-week dosing period all subjects (who did not discontinue assigned study drug or have not met criteria for loss of therapeutic response) will be provided the option to enroll into a separate Long Term Extension (LTE) study (GS-US-417-0304).

### 1.3. Sample Size and Power

Sample size is determined based on the superiority test of filgotinib in combination with MTX compared to MTX alone based on the change from Baseline in mTSS at Week 24. When assuming a difference of 0.62 between the two groups and a common standard deviation of 2.7, 400 subjects in the filgotinib 200 mg in combination with MTX group and 400 in the MTX alone group are required to obtain 90% power at a 2-sided 0.05-level.

The total sample size will be 1200 (400 subjects for filgotinib 200 mg in combination with MTX group, 200 subjects for filgotinib 100 mg in combination with MTX group, 200 subjects for filgotinib 200 mg alone group and 400 subjects for MTX alone group). This sample size will provide over 90% power to detect an increase in ACR20 response rate of 62% to 78% between the MTX alone group and each of the filgotinib groups respectively, using a 2-sided 0.05-level test.

## **2. TYPE OF PLANNED ANALYSIS**

### **2.1. Data Monitoring Committee Analyses**

An external multidisciplinary Data Monitoring Committee (DMC) will review the progress of the study and perform interim reviews of safety data in order to protect subject welfare and preserve study integrity. To ensure the best interests of the participants, the DMC will recommend to the sponsor if the nature, frequency, and severity of adverse effects associated with the study treatment warrant the early termination of the study, the continuation of the study, or the continuation of the study with modifications.

The initial review was conducted after approximately 100 subjects completed at least 12 weeks of dosing in any one of the three RA phase 3 studies (GS-US-417-0301, GS-US-417-0302, and GS-US-417-0303). Regular DMC review of safety data will be scheduled approximately every 6 months following the initial data review meeting including all 3 RA phase 3 studies and a long-term extension study (GS-US-417-0304).

The DMC's role and responsibilities and the scope of analysis to be provided to the DMC are provided in a mutually agreed upon charter, which defines the DMC membership, meeting logistics, and meeting frequency.

### **2.2. Week 24 Analysis**

A planned Week 24 analysis will be conducted after all subjects have either completed their Week 24 visit or prematurely discontinued from the study. A prespecified sponsorteam including members of which are not actively involved in the conduct of the study, will review the Week 24 unblinded safety and efficacy analysis results. A memo and a list will be maintained which document the individuals who have been granted access to the Week 24 unblinded results along with the justification for unblinding in accordance with Gilead SOPs. An interim analysis communication plan will be developed prior to unblinding. The Study Management Team with direct involvement in the conduct of the study will remain blinded to treatment assignments throughout the trial, until all subjects have completed the planned study Week 52 visits and the database has been locked.

### **2.3. Final Analysis**

After all subjects have completed the study, outstanding data queries have been resolved or adjudicated as unresolvable, and the data have been cleaned and finalized, the study blinding will be broken and the final analysis of the data will be performed.

### **3. GENERAL CONSIDERATIONS FOR DATA ANALYSES**

Analysis results will be presented using descriptive statistics. For categorical variables, the number and percentage of subjects in each category will be presented; for continuous variables, the number of subjects (n), mean, standard deviation (SD) or standard error (SE), median, first quartile (Q1), third quartile (Q3), minimum, and maximum will be presented.

All statistical tests will be 2-sided and performed at the 5% significance level unless otherwise specified.

By-subject listings will be presented for all subjects in the All Randomized Analysis Set and sorted by subject identification (ID) number, visit date, and time (if applicable). Data collected on log forms, such as AEs, will be presented in chronological order within the subject. The treatment group to which subjects were randomized will be included in the listings, as well as age, sex at birth, race, and ethnicity.

#### **3.1. Analysis Sets**

Analysis sets define the subjects to be included in an analysis. Analysis sets and their definitions are provided in this section. Subjects included in each analysis set will be determined before the study blind is broken for analysis. The analysis set will be identified and included as a subtitle of each TFL.

For each analysis set, the number and percentage of subjects eligible for inclusion, as well as the number and percentage of subjects who were excluded and the reasons for their exclusion, will be summarized by treatment group.

A listing of reasons for exclusion from analysis sets will be provided by subject.

##### **3.1.1. All Randomized Analysis Set**

All Randomized Analysis Set includes all subjects who are randomized in the study. This is the primary analysis set for by-subject listings.

##### **3.1.2. Full Analysis Set**

The Full Analysis Set (FAS) includes all randomized subjects who received at least 1 dose of study drug. The study drugs in this study are filgotinib 200 mg, filgotinib 100 mg, MTX, and PTMs. This is the primary analysis set for efficacy analyses.

##### **3.1.3. Per-Protocol Analysis Set**

The Per-Protocol (PP) Analysis Set includes subjects in the FAS who did not have major protocol deviations occurring prior to or at Week 24 which will affect the efficacy analysis, and were compliant (with on-treatment adherence  $\geq 80\%$  in the first 24-week period for all study drugs except MTX) to study treatment.

**Major protocol deviations** include the following

- Violate at least one of the following key eligibility criteria
  - 1) Have a diagnosis of RA (2010 ACR/EULAR criteria for RA), and are ACR functional class I-III
  - 2) Have  $\geq 6$  swollen joints (from swollen joint count based on 66 joints [SJC66]) and  $\geq 6$  tender joints (from tender joint count based on 68 joints [TJC68]) at both screening and Day 1 (need not be the same joints)
  - 3) Have serum CRP  $\geq 4$  mg/L
  - 4) Have limited or no prior treatment with MTX, ie, no more than 3 doses of MTX  $\leq 25$  mg each in the subject's lifetime for the treatment of RA, with the last dose at least 28 days prior to Day 1, and are an appropriate candidate for MTX therapy, as per investigator judgment
  - 5) Did not receive protocol prohibited medications
- Received prohibited concomitant medications
- Background medications were changed in violation of protocol
- Data were questionable because of significant site quality or compliance issues

Qualifications and identification of the specific major protocol deviations that result in exclusion from the PP Analysis Set will be determined while the study remains blinded, prior to database finalization.

The PP Analysis Set is the secondary analysis set for efficacy analyses on primary and key secondary endpoints. Statistical analyses using PP Analysis Set are specified in Section 6.

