3.2. Study Design

This is a randomized, double-blind, placebo- and active-controlled, Phase 3 study in adult male and female subjects with moderately to severely active RA who have limited or no prior exposure to MTX therapy. The study is designed to evaluate the efficacy, safety and tolerability of filgotinib as well as its effect on patient-reported outcomes, including work productivity, fatigue, and quality of life. In addition, PK will be assessed.

Adult male and female subjects with active RA will be screened to determine eligibility as per the inclusion and exclusion criteria (see Section 4.2 and 4.3, respectively). The Screening period will be up to 28 days. The screening window may be extended to up to 42 days prior to the Day 1 visit for subjects who require repeat collection of radiographs.

Written informed consent must be obtained before any study-related procedures take place. During the Screening period, following signing of the informed consent form (ICF), the subject's radiographs (hands, wrists, and feet) will be sent to central review for confirmation of joint erosion (see inclusion criterion 5; Section 4.2). Note that the subject's radiographs need to be sent to central review as soon as possible after completion and prior to Day 1 to allow for central reading and confirmation of one or more joint erosion in subjects that are seronegative.

Subjects will be randomized in a 2:1:1:2 ratio to filgotinib 200 mg plus MTX, filgotinib 100 mg plus MTX, filgotinib 200 mg alone, or MTX alone for up to 52 weeks in a double-blind fashion.

At Week 24, subjects who have not achieved a 20% improvement from Day 1 in both SJC and TJC will discontinue investigational therapy but will continue with study visits and assessments per protocol. All subjects who discontinue from investigational therapy are to receive standard of care treatment for their RA as determined by the investigator.

Responders at Week 24 will continue on the treatment regimens to which they were randomized through Week 52.

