4.2. Inclusion Criteria

Subjects must meet all of the following inclusion criteria to be eligible for participation in this study.

- 1) Male or female subjects who are ≥ 18 years of age, on the day of signing informed consent.
- 2) Have a diagnosis of RA (2010 ACR/EULAR criteria) ([Appendix 8](#)), and are ACR functional class I-III
- 3) Have ≥ 6 swollen joints (from a SJC66) and ≥ 6 tender joints (from a TJC68) at both Screening and Day 1 (need not be the same joints) ([Appendix 7](#))
- 4) Must meet at least one of the following parameters at Screening:
 - ≥ 1 documented joint erosion on radiographs of the hands, wrists or feet by central reading
 - OR
 - positivity for either RF or anti-CCP Ab (based on central laboratory)
 - OR
 - Serum CRP ≥ 4 mg/L (based on central laboratory)
- 5) Have limited or no prior treatment with MTX, ie, no more than 3 doses of MTX ≤ 25 mg each in the subject's lifetime for the treatment of RA, with the last dose at least 28 days prior to Day 1, and are an appropriate candidate for MTX therapy, as per investigator judgment
- 6) Females of childbearing potential (as defined in [Appendix 5](#)) must have a negative pregnancy test at Screening and Day 1
- 7) Male subjects and female subjects of childbearing potential who engage in heterosexual intercourse must agree to use protocol specified method(s) of contraception as described in [Appendix 5](#)
- 8) Lactating female subjects must agree to discontinue nursing from Screening through the end of their study participation.

9) Meet one of the following tuberculosis (TB) Screening criteria:

a) No evidence of active or latent TB:

- A negative QuantiFERON[®] TB-Gold In-Tube test at Screening and
- A chest radiograph (views as per local guidelines) taken at Screening or within the 3 months prior to Screening (with the report or films available for investigator review) without evidence of active or latent TB infection and
- No history of either untreated or inadequately treated latent or active TB infection

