8.2.1.2.2. Per-Protocol (PP) Analysis Set

The secondary analysis set for efficacy analyses will be the Per-Protocol (PP) Analysis set, which includes all subjects in the Full Analysis Set who have not committed any major protocol violation, including the violation of key entry criteria.

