### 3.4. Examination of Subject Subgroups

The primary and key secondary efficacy endpoints will be examined using the following subgroups (but not limited to the ones listed below):

- Age (on the first dosing date of any study drug, < 65 or ≥ 65)
- Sex at birth (male, female)
- Race
- Baseline weight ( < 60 kg, ≥ 60 to < 100 kg, ≥ 100 kg)
- Geographic region (A, B, C, or E)
- Presence of RF or anti-CCP Ab (Yes or No)
- Duration of RA diagnosis on the first dosing date of any study drug (< 1 year, ≥ 1 to < 2 years, ≥ 2 years)
- Disease activity at Baseline (DAS28[CRP] ≤ 5.1 or DAS28[CRP] > 5.1)
- Concurrent use of oral systemic corticosteroids on the first dosing date of any study drug (Yes or No)
- High-sensitivity C-reactive protein (hsCRP) at baseline (≥ 4 mg/L, < 4 mg/L)

Lists of oral systemic corticosteroids are provided in [Appendix 1](#).

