#### **6.2.4.1. Per-Protocol Analysis**

To evaluate the impact of study conduct on the primary analysis, the proportion of subjects who achieve ACR20 at Week 24 will be analyzed based on the PP Analysis Set as defined in Section 3.1.3 using the logistic regression analysis with NRI for the comparisons of filgotinib dose groups versus MTX alone group. The 2-sided 95% CI of the ACR20 response rate at Week 24 based on normal approximation for each treatment group will be provided.

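### SAP 3.1.3 cuts the three-way entry criterion down to CRP ≥ 4 mg/L alone, so eligible subjects with low CRP drop out of the Per-Protocol set

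*SAP*

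**What the plan says.** **Protocol.** Section 4.2, criterion 4, says that subjects "Must meet at least one of the following parameters at Screening". It then gives three routes joined by OR: at least one erosion on central reading, RF or anti-CCP positivity at the central laboratory, or serum CRP of 4 mg/L or more at the central laboratory. The synopsis lists the same three routes. Section 1.3.1 has the same either/or structure, although it speaks only of raised CRP and gives no cut-off. Section 3.2 asks for radiographs to be sent early to allow "confirmation of one or more joint erosion in subjects that are seronegative". Section 8.2.1.2.2 defines the Per-Protocol (PP) set as FAS subjects "who have not committed any major protocol violation, including the violation of key entry criteria".

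**SAP.** Section 3.1.3 removes from the PP set subjects with major deviations up to Week 24 that affect the efficacy analysis, and subjects with adherence below 80%. The first kind of major deviation is to "Violate at least one of the following key eligibility criteria". Five items follow. Item 3) is "Have serum CRP" of at least 4 mg/L and nothing more: no erosion or serology route, no time point and no laboratory. The section ends by stating that "Qualifications and identification of the specific major protocol deviations that result in exclusion from the PP Analysis Set will be determined" under the blind, before database finalization.

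The PP set is used in Section 6.2.4.1, whose stated purpose is "To evaluate the impact of study conduct on the primary analysis", and in Section 6.3.3.1 for all key secondary endpoints.

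**The concern.** A subject who enters on serology or erosion with CRP below 4 mg/L has satisfied the protocol in full, yet fails item 3). Under the SAP's own wording, that makes the subject a major deviator.

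Two things are at stake. First, the PP analysis would stop answering its stated question. A difference between PP and FAS results should reflect how the study was conducted. With item 3) as written, it could also reflect removal of the low-CRP part of the intended population, and CRP is a component of both ACR20 and DAS28(CRP). Second, the reporting would be wrong. SAP Section 3.1 calls for exclusions and their reasons by treatment group, so eligible subjects would be tabulated as having broken an entry criterion. The eligibility table in SAP Section 4.3 would not list them as having failed criterion 4.

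**Working it through.** The plan gives no figure for this point, so the check compares the two rules.

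**1. Placement of item 3).** Setting the SAP list against Protocol Section 4.2:

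| SAP 3.1.3 item | Protocol criterion | Match |
|---|---|---|
| 1) diagnosis and functional class | 2 | near-verbatim |
| 2) joint counts, Screening and Day 1 | 3 | near-verbatim, time points kept |
| 3) CRP ≥ 4 mg/L | 4 | one of three routes; time point and laboratory dropped |
| 4) prior MTX | 5 | near-verbatim |

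Item 3) stands where criterion 4 belongs and is the only one of these four that has been shortened.

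**2. The two rules.** Protocol: eligible if erosion OR seropositive OR CRP ≥ 4. SAP item 3): met only if CRP ≥ 4. Three yes/no markers give 2 × 2 × 2 = 8 combinations.

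| Erosion | Seropositive | CRP ≥ 4 | Protocol criterion 4 | SAP item 3) |
|---|---|---|---|---|
| no | no | no | not met | not met |
| no | no | yes | met | met |
| no | yes | no | met | **not met** |
| no | yes | yes | met | met |
| yes | no | no | met | **not met** |
| yes | no | yes | met | met |
| yes | yes | no | met | **not met** |
| yes | yes | yes | met | met |

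The protocol admits 8 − 1 = 7 combinations. Item 3) fails 3 of those 7. With the full criterion restored, it fails 0 of 7. These are combinations, not subjects, and they are not equally common.

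**3. Time point.** CRP is drawn at Screening (Protocol 6.2.1) and on Day 1 (Protocol 6.2.2). Criterion 4 uses Screening; item 3) does not say which value counts. SAP Section 3.8.2 takes baseline as the last value on or before first dose, which will usually be Day 1. If item 3) were programmed on baseline CRP, a subject who qualified by CRP at Screening and then fell below 4 mg/L would also be classed as a deviator. The literal rule can therefore give two different PP sets.

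**4. Declared change?** SAP Section 6.5 lists three changes: logistic regression in place of the Cochran-Mantel-Haenszel test, two added key secondary endpoints, and a reordered hierarchy. A CRP restriction on the PP set is not among them.

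**The case against.** The strongest reply is that nobody need be excluded. Section 3.1.3 limits exclusion to deviations that affect the efficacy analysis and leaves the final list to blinded review. An eligible subject has no protocol deviation to review, so item 3) can be read as shorthand for criterion 4. That may be how it works out in practice. But item 3) names the CRP threshold itself as the criterion, and a programmer following the text would flag these subjects. Review that has to override the written rule does not repair it.

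Several narrower points stand:

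- If applied to Screening CRP, the selection happens before randomization and does not by itself unbalance the arms. It narrows the population.
- The SAP 3.4 subgroup, "High-sensitivity C-reactive protein (hsCRP) at baseline" split at 4 mg/L, concerns baseline. A subject could enter on Screening CRP and be below 4 mg/L later, so the subgroup does not prove that the SAP expected entry by the other routes. It would, however, show results by CRP level, and the exclusion listing would make the loss visible.
- Protocol 3.2 is a logistics instruction. It shows that the erosion route was provided for, not how often it was used.
- Silence in Section 6.5 is weak evidence alone, since the 80% adherence rule is not listed there either.
- The CRP term of DAS28(CRP) at the cut, 0.36 × ln(4 + 1) = 0.58, only restates the threshold. It says nothing about the effect on a Week 24 result.

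None of these changes the mismatch between item 3) and criterion 4.

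**Conclusion.** The concern holds. Read as written, SAP 3.1.3 item 3) contradicts Protocol inclusion criterion 4 and removes from the PP set subjects who met every entry requirement: those with an erosion, positive serology or both, and CRP below 4 mg/L. By rule this is 3 of the 7 admitted combinations. The number of subjects, and the effect on any estimate, cannot be computed without the share of enrolled subjects with low CRP.

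The conclusion rests on the literal text and assumes that blinded review does not override it. The reach is limited to the PP sensitivity analyses of the primary and key secondary endpoints. The FAS analyses and the testing hierarchy are unaffected. It should be corrected, but it does not threaten the primary conclusion.

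**What to change.** Rewrite item 3) so that it carries inclusion criterion 4 whole: at Screening, any one of an erosion on central reading, RF or anti-CCP positive at the central laboratory, or serum CRP of 4 mg/L or more at the central laboratory. If a CRP-restricted PP set is really intended, say so in SAP Section 6.5, give the reason, and state which CRP value applies.

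The cost is one line of SAP text. The Screening serology, radiograph readings and CRP are already collected for eligibility. The change should be made before the Week 24 database is finalized and before anyone sees unblinded Week 24 results.
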